1.7.2 Exploratory Biomarkers-Tumor Tissue

1.7.2.1 RNA-seq (both baseline and in the end of cycle 1, beginning of cycle 2 (day 22 \pm 2 days), immediately before concurrent entinostat-pembrolizumab treatment day 22 \pm 2 days).

RNA will be extracted from FFPE tissue sections from both archived in the end of cycle 1, beginning of cycle 2 (day 22 \pm 2 days), immediately before treatment for sequencing analysis. RNA-seq on paired baseline and on day 22 \pm 2 treatment tissues will assist in: (a) identifying transcription signatures that are associated with non-inflamed melanomas, such as IPRES and immune low signatures (baseline), type I interferon response, IPRES and epigenetic signatures (day 22 versus baseline) ^{2,3,13}. Secondly, (b) perform a somatic mutation calling (expressed mutations) analysis, in particular for genes encoding for epigenetic modifiers (e.g. *SMARCA4*, *PBRM1*, *ARID1A*, *ARID2*, *ARID1B*, *DNMT3A*, *TET2*, *MLL1/2/3*, *NSD1/2*, *EZH2*, *SETD2*, *BRD4*) and epigenetic regulators (e.g. *OCT4*, *NANOG*, *LIN28*, *SOX2*, *KLF4*). We predict that inactivating mutations in any of these genes may have impact in chromatin accessibility, as has been previously published in renal cell carcinoma from UNC-CH investigators ¹³⁴, and therefore these tumors may differentially respond to HDAC inhibition. RNA-seq is also ideal for detection of aberrant splicing and expressed immunogenic neoepitopes ¹³⁵ ([name] UNC-CH, unpublished data). This process can therefore help us study immunogenicity of tumors that may have a low somatic tumor burden. It is therefore quite possible that HDAC inhibition may change RNA expression of genes that may have low or absent expression at baseline due to widespread RNA processing defects, but

upon treatment with a HDACi, RNA expression of these genes may be significantly upregulated leading to increased expression of neoepitopes. Thirdly, (c) analyze the immune receptor repertoire (richness, observed V-J rearrangements; clonality, evenness of the repertoire based on frequencies of specific V-J rearrangements) within tumors. The T-cell receptor (TCR) repertoire in peripheral blood has been previously associated with response to immune checkpoint inhibitors¹³⁶⁻¹³⁹. We postulate that TCR and B-cell receptor (BCR) repertoire analysis within tumor tissue will yield more specific TCR/BCR clones that are associated with immune response in the end of cycle 1, beginning of cycle 2 (day 22±2 days), immediately before treatment samples from the prospective responders, compared to the prospective non-responders.

1.7.2.2 Formaldehyde-assisted isolation of regulatory elements (FAIRE; baseline and on day 22).

In tumors, organization of the chromatin landscape offers a comprehensive overview of the rewiring of transcriptional networks that accompany processes such as cellular differentiation, tumor growth, metastasis, and therapeutic resistance, which can be more reliable in predicting cell behavior than gene expression profiles alone^{140,141}. Further, it has been shown that chromatin accessibility changes can be detected in cancer cells following treatment with small molecule inhibitors¹⁴²⁻¹⁴⁴. Therefore, tumor-specific chromatin signatures may offer remarkable diagnostic and biomarker potential. We will use a protocol developed by the [name], [name], and [name] labs at UNC-CH to extract DNA accessible chromatin from formalin-fixed, paraffin-embedded (FFPE) tissue. These DNA regions harbor regulatory elements (active transcriptional start sites, transcriptional enhancers, insulators, silencers, and locus control regions). Chromatin signatures will be determined by performing FAIRE, a biochemical technique that purifies accessible chromatin from formalin-fixed samples, followed by high-throughput sequencing.

1.7.2.3 Tissue-imaging studies

1.7.2.3.1 Expression of PD-L1 (melanoma cells and immune cells), MHC class I (melanoma cells) and CD8+ cells at baseline and on day 22, using multicolor immunofluorescence (IF). If our integrated biomarker of assessing TIL/TAL is correct, we do not anticipate detecting any CD8+ cells at baseline; in fact, a proportion of these non-inflamed melanomas may have no expression of MHC class I. However, in the end of cycle 1, beginning of cycle 2 (day 22±2 days), immediately before concurrent pembrolizumab-entinostat treatment, we anticipate that HDAC inhibition in those melanomas that have TIL/TAL present, based on the H&E analysis (integral biomarker), to also contain CD8+ cells. In addition, we anticipate that melanoma cells in patients who respond to concurrent entinostat-pembrolizumab will express both MHC class I+ and PD-L1, which have been previously shown to be upregulated in response to HDACi.

1.7.2.3.2 Expression of global histone modification markers: acetylated histone 3 lysine 18 (H3K18Ac), acetylated histone 4 lysine 12 (H4K12Ac), dimethylated histone 4 arginine 3 (H4R3diMe), dimethylated histone 3 lysine 4 (H3 K4diMe), (H3K27triMe) in tumor specimens by single-color immunohistochemistry (IHC) will be important due to previous reports about association between global histone modification levels and prognosis^{145,146}. Both archived/baseline and day 22 samples will be stained to assess both prediction of response to entinostat as well as entinostat-associated changes in global histone modifications. We anticipate that at least the global histone acetylation markers H3K18Ac and H4K12Ac to be high at baseline in a subset of patients whose melanomas convert from ‘non-inflamed’ to ‘inflamed’ and that 21±2 days of entinostat priming will significantly suppress H3K18Ac and H4K12Ac. Lack of suppression of the histone acetylation markers may suggest inadequate target inhibition by entinostat.

1.7.2.3.3 Expression of entinostat targets HDAC1, HDAC2, HDAC3 in archived-baseline tumor tissues only by single-color IHC will be examined due to reports about heterogeneous expression of HDAC1, HDAC2, and HDAC3 in melanoma⁶⁶. We would like to investigate whether expression of any of these targets, HDAC1, HDAC2, HDAC3, is associated with treatment response to the entinostat-pembrolizumab combination.

1.7.2.4 Exploratory Biomarkers-Peripheral blood mononuclear cells (PBMC; baseline, in the end of cycle 1, beginning of cycle 2 (day 22±2 days), immediately before concurrent entinostat-pembrolizumab; week 10; and end of treatment):

- a. It is quite possible that entinostat will have an indirect immunomodulatory effect on immune cell subsets, much like the suppression of peripheral blood MDSC in breast cancer patients⁸⁴. We plan to perform multi-parameter flow cytometry on PBMCs to identify various immunoregulatory cell subsets (e.g. monocytic and granulocytic MDSCs, T reg cells).
- b. Assess Histone H3 and H4 acetylation in PBMCs by peripheral blood multi-parameter flow cytometry^{147,148}. In the ENCORE 301 trial patients bearing peripheral immune cell subsets (T cells, B cells, monocytes) that were found to be hyperacetylated and were treated with entinostat and exemestane lived longer compared to non-acetylators. It would be interesting to see if TIL/TAL-absent melanomas that convert from absent TIL/TALs before entinostat treatment to TIL/TAL-present tumors following 21 days of entinostat monotherapy exhibit (a) higher levels of H3 and H4 acetylation in peripheral blood compared to non-converters at baseline b) undergo the greatest changes in acetylation between baseline and day 22, immediately prior to pembrolizumab treatment.

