Reversible acetylation of lysine residues on the tails and other more internal residues of histone proteins, H3 and H4 (e.g. H3K9, H3K14, H4K5, H4K16), is the best studied type of histone modification and is catalyzed by the transfer of acetyl group from acetyl-CoA to the ϵ -amino group at the terminal of the lysine side chain by means of histone acetyl transferases (HAT). The addition of the acetyl group neutralizes the lysine’s positive charge, thereby weakening the interaction with the negatively charged DNA, and leads to a more open chromatin structure allowing easier access to transcription factors and increased transcription. Histone acetylation also influences transcription by acting as a binding target for histone reader groups and regulates (prevents) deposition of other histone marks, such as the transcriptionally permissive H3K4me3 or the repressive H3K27me3 modification⁶³. On the other hand, these acetyl groups are removed by histone deacetylases (HDACs). HDACs are divided into 4 classes on the basis of structural homology to yeast HDACs, mechanism of enzyme activity, and cellular localization. The ‘classic’, or type I, are ubiquitously expressed in all cell types and mostly localized to the nucleus (1, 2, 3, and 8). Type II are more restricted in distinct

cell types (smooth muscle, heart, pancreas, and brain) and shuttle between the nucleus and cytosol (4, 5, 6, 7, 9, and 10). Type III (NAD-dependent sirtuins 1-7) possess dual enzymatic activity that includes mono-ADP-ribosyltransferase, in addition to the HDAC activity. In addition, type III HDACs have various subcellular organizations other than the nucleus (cytoplasm, mitochondria, and nucleolus). Class IV HDACs have similar localization to class II (HDAC11)⁶⁴.

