1.4.6 Entinostat

1.4.6.1 Non-Clinical studies

Entinostat (pyridine-3-yl)methyl((4-[(2-aminophenyl)carbamoyl]phenyl)methyl) carbamate), or SNDX-275, MS-275 is an orally available inhibitor of HDACs 1, 2, 3, and 11 [IC₅₀ (nM) 124, 139, 187, 427, respectively]. The selectivity of entinostat for these HDAC isoforms may account for its better safety and efficacy compared to other nonselective pan-HDAC inhibitors^{87,88}. Exposure of various cancer cell lines to entinostat resulted in accumulation of hyperacetylated histones at concentration between 0.3-1 μM and gene expression changes in various cell processes, such as cell growth, apoptosis, differentiation, cell communication, regulation of transcription, cell signaling, and chromosome organization. Entinostat demonstrated broad, dose-dependent, tumor-inhibitory effects against cancer cell lines with IC₅₀ values ranging between 0.04-4.71 μM. Entinostat showed tumor growth inhibition in human tumor xenografts from diverse cancer types, such as melanoma, non-small cell lung cancer, and breast cancer. The maximum tolerated dose in the animal experiments was 50mg/kg daily.

As predicted by its epigenetic mechanism of action, entinostat may restore sensitivity in resistant cancer cell lines *in vitro* and *in vivo* when combined with various classes of anticancer agents, such as chemotherapies, anti-estrogens, EGFR inhibitors, DNA methyltransferase (DNMT) inhibitors and immunotherapies.

Examples of entinostat in combination with hormonal therapies (aromatase inhibitor, selective estrogen modulators) and DNA methylase transferase inhibitors ('dual epigenetic blockade') are provided in the Investigators' Brochure and elsewhere^{89,90}.

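### Section 1.7.2.3.2 reads a failure of tumor H3K18Ac and H4K12Ac to fall as possible under-inhibition by entinostat, while the protocol's own mechanism text points to a rise; the sections need reconciling

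*Combined protocol and SAP*

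**What the plan says.** Section 1.7.2.3.2 lists five marks for single-color immunohistochemistry on archived/baseline and day 22 tumor: H3K18Ac, H4K12Ac, H4R3diMe, H3K4diMe and H3K27triMe. One stated purpose is to assess "entinostat-associated changes in global histone modifications". For the acetylation marks it goes further. It expects "H3K18Ac and H4K12Ac to be high at baseline in a subset of patients whose melanomas convert" and, for the on-treatment sample, that about three weeks of treatment, in its words "days of entinostat priming will significantly suppress H3K18Ac and H4K12Ac". It then gives the interpretation: "Lack of suppression of the histone acetylation markers may suggest inadequate target inhibition by entinostat".

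The background describes the biology as follows.

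- Section 1.4.2 introduces "Reversible acetylation of lysine residues on the tails and other more internal residues of histone proteins, H3 and H4 (e.g. H3K9, H3K14, H4K5, H4K16") as the best-studied histone modification, and says that "these acetyl groups are removed by histone deacetylases (HDACs").
- Section 1.4.6.1 says entinostat "is an orally available inhibitor of HDACs 1, 2, 3, and 11", and that "Exposure of various cancer cell lines to entinostat resulted in accumulation of hyperacetylated histones".

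The heading of Section 1.7.2 labels these tumor markers exploratory. Section 9.3 lists tumor imaging at baseline and day 22 among the secondary correlative endpoints. Section 9.3.4 refers back to Section 1.7.2.3 for the description and applies quantitative computer image analysis; the rest of it is redacted.

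**The concern.** If an enzyme removes a chemical group and a drug blocks that enzyme, the simplest expectation is that the group is kept or accumulates. Section 1.7.2.3.2 expects the reverse and treats absence of the reverse as a possible sign that the drug missed its target.

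What is at stake is the target-engagement reading of this stain. If few tumors convert, a natural question is whether entinostat failed to inhibit HDACs in the tumor or inhibited them without effect. I found no other readable sentence saying how inadequate inhibition in tumor would be recognised. Followed as written, the sentence could put a tumor showing the direction implied by Sections 1.4.2 and 1.4.6.1 in the possibly under-inhibited group, and a tumor whose acetylation fell in the adequately inhibited group.

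**Working it through.** The plan gives no figure to reproduce here: the readable text has no cut-off, test or sample-size statement for these marks. The check sets the stated directions side by side.

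1. **Section 1.7.2.3.2, tumor, day 22 against baseline.** Expected direction for H3K18Ac and H4K12Ac: down. Not going down: possible inadequate inhibition.
2. **Section 1.4.2, mechanism.** HDACs remove acetyl groups from H3 and H4 lysines. Blocking removal implies acetylation is preserved or goes up.
3. **Section 1.4.6.1, drug.** Entinostat inhibits HDACs 1, 2, 3 and 11. Combined with step 2, the implied direction is preserved or up.
4. **Section 1.4.6.1, observation.** Direction reported in cancer cell lines exposed to entinostat: up.
5. **Section 1.7.2.4, blood.** It asks whether converters have higher H3 and H4 acetylation at baseline and whether they show the largest change by day 22, without giving a direction for that change. It also cites an earlier entinostat-exemestane trial in which patients with hyperacetylated blood cells lived longer than those without. This sits more easily with a rise but does not settle what happens in tumor.

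Steps 2 to 4 agree with each other and conflict with step 1.

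**Does timing explain a fall?** By the dosing schema in Section 5.2.1, the last scheduled dose before the day 22 biopsy is on day 15, and Section 7.4.2 places the day 22 dose after the biopsy. The gap is 22 − 15 = 7 days, or 7 × 24 = 168 hours. Section 1.4.6.2.1 gives a mean terminal half-life of about 194 hours, so the scheduled gap is less than one half-life. Simple fading of the drug effect would in any case return the marks towards baseline; it would not by itself predict levels below baseline.

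**Extent.** Marks with a stated expected fall: 2 of 5. The three methylation marks carry no stated direction.

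**The case against.** The strongest reply is that the mechanism text is general. The residues named in Section 1.4.2 are H3K9, H3K14, H4K5 and H4K16, not H3K18 or H4K12, and the finding in Section 1.4.6.1 is in cell lines, not melanoma tissue after three weekly doses. A late or indirect fall in particular marks is not excluded. This stands. A reader might infer that the documents establish a rise in these two marks in treated tumors; they do not. They show an expectation that conflicts with the protocol's own general account and is not explained. The residues in Section 1.4.2 are, however, given only as examples, and Section 1.4.6.1 does not restrict its statement to particular residues.

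Second, the disputed text is a hedged expectation in the correlative rationale. Readable Section 9 attaches no cut-off, one-sided test or patient classification to it, and quantitative imaging would show a rise if there were one. This also stands, and it limits the consequence to interpretation.

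Third, a reader might infer that the trial's account of why tumors convert would be wrong. The documents do not support that. Section 1.1 and Section 1.7.2.3.2 connect these marks to conversion mainly through their baseline level, which does not depend on the direction of change.

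Finally, parts of Sections 9.3 and 9.3.4 and the exploratory objectives and endpoints are redacted and may hold a clarification. Even so, Section 9.3.4 sends the reader back to Section 1.7.2.3 for the description, so the sentence there would still need to agree with it.

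**Conclusion.** The inconsistency is real in the readable text and should be corrected before the stains are interpreted. Section 1.7.2.3.2 gives the two acetylation marks an expected direction opposite to the one implied by Sections 1.4.2 and 1.4.6.1, without a reason, and hangs a target-engagement reading on it.

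The size is small: one hedged sentence, 2 of 5 marks, an exploratory stain. The primary endpoint is H&E conversion, judged by at least 3 of 10 evaluable patients, with a stated type I error of 0.04 at a true rate of 0.08 and power of 83% at 0.4 (Section 9.2). None of this uses the histone marks and none of it changes. Treatment does not depend on them either.

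The conclusion assumes that the general statements about H3 and H4 are meant to apply to H3K18 and H4K12, and that the redacted text gives no rationale for a fall. If there is such a rationale, the defect is that it is missing from the section that describes the stain. Confidence is high for the textual conflict and lower for any practical harm, because the documents do not say how the reading would be applied.

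**What to change.** Before the stains are interpreted, reconcile Section 1.7.2.3.2 with Sections 1.4.2 and 1.4.6.1 in one of two ways:

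- replace the expectation and reading with ones consistent with the mechanism text, so that lack of an increase, rather than lack of suppression, may suggest inadequate inhibition; or
- keep the expected decrease and give the rationale for it in these two marks in tumor tissue.

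In either case, report each patient's paired baseline to day 22 change as a signed quantitative value alongside the baseline level, so that neither direction is automatically read as failed inhibition. Keeping the value continuous avoids having to define what counts as no change.

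The cost is rewording two sentences and adding one descriptive listing. Both time points are already stained and Section 9.3.4 already plans quantitative image analysis, so no new samples, assays or visits are needed.

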2.0 STUDY OBJECTIVES

2.1 Primary Objective

Assess the incidence of conversion of non-inflamed (TIL/TAL-absent by histopathologic analysis of H&E-stained tissue section from archived metastatic melanoma tumors) to inflamed melanomas following 3 weeks of entinostat monotherapy by performing histopathologic analysis of representative H&E-stained tissue sections from melanoma tumors before treatment and in the end of cycle 1, beginning of cycle 2 (day 22±2 days), immediately before concurrent pembrolizumab-entinostat treatment on day 22 (±2 days) following single-agent entinostat treatment.

2.2 Secondary Objectives

- 2.2.1 Assess antitumor response rate to the pembrolizumab-entinostat combination in patients with ‘non-inflamed’ melanomas (TIL/TAL-absent by histopathologic analysis of H&E-stained tissue section from archived metastatic melanoma tumors) irrespective of prior PD-1/PD-L1 inhibitor treatment status after 3 cycles (9 weeks) of study treatment by RECIST v1.1 criteria.
- 2.2.2 Assess the 6-month (i.e. 27 weeks) progression-free survival (PFS) rate in patients with ‘non-inflamed’ (TIL/TAL-absent), irrespective of prior PD-1/PD-L1 inhibitor treatment status treated with the pembrolizumab-entinostat combination by RECIST v1.1 criteria.
- 2.2.3 Assess toxicity of the concurrent pembrolizumab-entinostat combination based on NCI-CTCAE v.5.0.

2.3 Exploratory Objectives

2.3.1

[REDACTED]

2.3.2

[REDACTED]

2.3.3

[REDACTED]

[REDACTED]

3.0 Criteria for Evaluation / Study Endpoints

3.1 Primary Endpoint

Change in immunogenicity in response to entinostat priming will be determined by performing histopathologic analysis of H&E-stained tumor sections collected at baseline and following one cycles of entinostat, immediately prior to begin dosing patients with pembrolizumab.

3.2 Secondary Endpoints

- 3.2.1 The ORR (CR + PR) at 10 weeks will assessed based on RECIST v1.1 criteria.
- 3.2.2 PFS rate at approximately 6 months (i.e. 27 weeks) is defined as the time from day 1 of treatment until disease progression or death status measured 6 months after initiating study treatment. Progression events will be defined per RECIST v1.1 criteria.
- 3.2.3 The toxicity will be assessed based on the NCI CTCAE v 5.0 criteria. For example, the incidence of AEs that occur in subjects enroll who receive at least one dose of therapy.

3.3 Exploratory Endpoints

3.3.1 [REDACTED]

3.3.1 [REDACTED]

3.3.2 [REDACTED]

[REDACTED]

3.3.3 [REDACTED]

4.0 PATIENT ELIGIBILITY

In order to participate in this study a subject must meet ALL of the eligibility criteria outlined below.

4.1 Inclusion Criteria

- 4.1.1 Age \geq 18 years at the time of consent.
- 4.1.2 Subject has provided informed consent and HIPAA prior to initiation of any study-specific activities/procedures.
- 4.1.3 ECOG Performance Status of ≤ 2 .
- 4.1.4 Histologically confirmed metastatic (regional or distant) melanoma of any subtype (cutaneous, mucosal, ocular).
- 4.1.5 AJCC stage unresectable III or stage IV disease that is measurable by RECIST v1.1 criteria.
- 4.1.6 Must agree to undergo one on-treatment tumor biopsy on day 22 (± 2 days) of the study. Subjects for whom fresh samples cannot be safely provided (e.g., inaccessible tumor for biopsy) will not be eligible for study participation.
- 4.1.7 Must have available archival tissue and subjects must have consented to allow collection of archived tumor blocks from previous surgeries confirming or treating unresectable stage III or distant metastatic disease. If more than one archived tumor block is available, only one block is required to be analyzed for the presence of TIL/TALS. Archived tumor tissues must fulfill the following criteria based on two representative H&E-stained tissue sections: (1) the tumor surface area must be at least 1cm^2 (which can be from a combination of metastatic blocks if necessary), (2) no more than 20% of necrosis, (3) the ratio of viable tumor cells to tumor-associated stroma should be at least 60/40, and (4) if TILs are present based on H&E stained

sections, they must be $\leq 1\%$ of the total number of cells in the specimen; the amount of tissue should be ≥ 1 cm².

[name], study pathologist, must sign off on the eligibility of archived tumor blocks before study enrollment. If archival tissue is unavailable or insufficient, fresh biopsy should be performed to confirm unresectable stage III or distant metastatic disease.

4.1.8 Previous treatment with immune checkpoint inhibitors and chemotherapies is allowed on condition that the last treatment is at least 28 days prior to first dose of entinostat. Previous treatment with targeted therapies (e.g. MAPK inhibitors) is allowed on condition that the last treatment was administered at least 15 days prior to first dose of entinostat).

4.1.9 Demonstrate adequate organ function as defined in the table below; all screening labs to be obtained within 21 days prior to entinostat treatment.

System	Laboratory Value
Hematological*	
Hemoglobin (Hgb)	≥ 9 g/dL or ≥ 5.6 mmol/L without transfusion or erythropoietin dependency (within 7 days of assessment of Hgb)
Absolute Neutrophil Count (ANC)	$\geq 1,500/\text{mm}^3$
Platelets	$\geq 100,000/\text{mm}^3$
Renal*	
Creatinine	≤ 1.5 x upper limits of normal (ULN) OR
Measured or calculated ¹ creatinine clearance (CrCl) (glomerular filtration rate [GFR] can also be used in place of creatinine of CrCl)	≥ 60 mL/min using the Cockcroft-Gault formula for subjects with creatinine levels > 1.5 x institutional ULN
Hepatic*	
Bilirubin	≤ 1.5 xULN OR Direct bilirubin \leq ULN for patients with total bilirubin levels >1.5 xULN
Aspartate aminotransferase (AST)	≤ 2.5 xULN OR < 5 xULN for subjects with liver metastases
Alanine aminotransferase (ALT)	≤ 2.5 xULN OR < 5 xULN for subjects with liver metastases
Albumin	≥ 2.5 mg/dL
Coagulation*	

System	Laboratory Value
International Normalized Ratio (INR) or Prothrombin Time (PT)	≤1.5xULN, unless subject is receiving anticoagulant therapy as long as PT or PTT is within therapeutic range of intended use of anticoagulants
Activated Partial Thromboplastin Time (aPTT)	≤1.5xULN, unless subject is receiving anticoagulant therapy, as long as PT or PTT is within therapeutic range of intended use of anticoagulants

*Note: Hematology and other lab parameters that are ≤ grade 2 BUT still meet criteria for study entry are allowed. Furthermore, changes in laboratory parameters during the study should not be considered AEs unless they meet criteria for dose modification(s) of study medication outlined by the protocol in Section 5.3.1 and/or worsen from baseline during therapy.

4.1.10 A female of childbearing potential must have a negative serum pregnancy test during screening and a negative urine pregnancy test within 3 days prior to receiving the first dose of study drug. If the screening serum test is done within 3 days prior to receiving the first dose of study drug, a urine test is not required. A female of childbearing potential must agree to use effective contraception during the study and for 120 days after the last dose of study drug. A female of non-childbearing potential defined as (by other than medical reasons):

- ≥45 years of age and has not had menses for >2 years,
- Amenorrheic for <2 years without a hysterectomy and oophorectomy and a follicle-stimulating hormone value in the postmenopausal range upon pre-study (screening) evaluation,
- Post hysterectomy, oophorectomy or tubal ligation. Documented hysterectomy or oophorectomy must be confirmed with medical records of the actual procedure or confirmed by an ultrasound. Tubal ligation must be confirmed with medical records of the actual procedure; otherwise the patient must be willing to use 2 adequate barrier methods throughout the study, starting with the screening visit through 120 days after the last dose of entinostat,
- If male, agrees to use an adequate method of contraception starting with the first dose of study drug through 120 days after the last dose of entinostat,
- See section 5.6.2 for information on acceptable methods of contraception.

4.1.11 Experienced resolution of toxic effect(s) of the most recent prior anti-cancer therapy to Grade ≤1 (except alopecia or neuropathy) by CTCAE v5.0. Exceptions

are patients who may have developed autoimmune-type side effects that require permanent hormonal replacement from previous therapies.

- 4.1.12 If the patient underwent major surgery or radiation therapy, these procedures must have occurred at least 15 days prior to the first dose of entinostat. In addition, patients must have recovered from the toxicity and/or complications from the intervention to Grade ≤ 1 .
- 4.1.13 Subjects must be willing and able to comply with study procedures based on the judgement of the investigator or protocol designee.

